7.7.7 Withdrawal from the study and study evaluation completion

Patients may voluntarily withdraw from the study or be dropped from it at the discretion of the investigator at any time.

As a general rule, if a patient discontinues study drug and later is withdrawn from the study, the reasons for study evaluation completion may include the following:

- Protocol deviation
- Subject withdrew consent
- Lost to follow-up
- Death
- Use of non-study systemic anti-PTEN therapy
- Administrative problems

For patients who are lost to follow-up, the investigator should show due diligence by documenting in the source documents steps taken to contact the patient, e.g., dates of telephone calls, registered letters, etc.

7.7.8 Study Discontinuation

The National Institutes of Health (NIH), Data and Safety Monitoring Committee (DSMC) and local IRBs (at their local site) have the authority to stop or suspend this trial at any time. This study may be suspended or closed if:

- Early stopping rules have been met
- · Accrual has been met
- The study objectives have been met
- The Study Chair / Study Investigators believe it is not safe for the study to continue
- The DSMC suspends or closes the trial
- The NIH suspends or closes the trial
- The FDA suspends or closes the trial

7.8 Good Clinical Practice and Human Subjects Training

All personnel conducting human research as part of the Consortium will have completed an approved training course on human subjects' protection as required by their local institution; training is updated, and will be current at the time they are engaged in Consortium clinical activities. All personnel are required to read and agree to adhere to the FDA Good Clinical Practice Guidelines. Documentation of trainings will be maintained by each site in their regulatory binder.

7.9 Neuropsychological Evaluations

The measures included were selected to cover the full age range included in the trial. This combination of age and developmental level does mean that floor or ceiling effects may be seen in a small proportion of study participants on some of the measures. The approach in the study will be to use very experienced testers to administer measures. The testers will be asked to attempt all direct measures on all participants, with the acknowledgement that, in some instances it may not be possible to complete all tasks. All measures will be readministered as per study protocols, regardless of previous floor or ceiling effects.

7.9.1 Training and Reliability of Independent Evaluations (IEs)

At each site, an experienced team will conduct study procedures guided by an operations manual. IEs, who are blind to treatment condition, will rate 3 measures in this study: CGI-S, CGI-I, and ADOS-2. Similar to previous studies, IEs will be trained to reliability criterion on the CGI-S, CGI-I, and ADOS-2 on 3 to 4 vignettes at the start and yearly after that ^{42,43}_ENREF_16. If IEs fail to meet reliability criterion, they will be re-trained and given a second set of 3 vignettes for scoring. This procedure will be repeated as necessary to ensure that each rater has demonstrated reliability.

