6.3 Known Undesirable Effects of Study Drug/Treatment

Overall, safety data available from completed, controlled and uncontrolled studies indicate that everolimus is generally well tolerated at weekly or daily doses. The safety profile is characterized by manageable adverse events (AEs). These AEs are generally reversible and non-cumulative.

Adverse events most frequently observed with everolimus are stomatitis, mouth ulcers, acne, infection, and menstrual irregularities. Adverse events that are also common include: rash, diarrhea, fatigue, asthenia, nausea, peripheral edema, decreased appetite, headache, dysgeusia, epistaxis, mucosal inflammation, pneumonitis, weight decreased, vomiting, pruritus, cough, dyspnea, dry skin, nail disorder, aggression, and pyrexia.

Overall, the most frequently observed laboratory abnormalities include: decreased hematology parameters including hemoglobin, lymphocytes, platelets, and neutrophils; increased clinical chemistry parameters including cholesterol, triglycerides, glucose, aspartate transaminases, creatinine, alanine transaminases, and bilirubin; and decreased clinical chemistry parameters including phosphate and potassium.

The majority of these AEs have been of mild to moderate severity (NCI CTC grade 1-2). Recommendations for dose adjustments, should any of these treatment related adverse events occur, are given in Table 3.

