6.3.7 Management of Mouth Ulcers/Stomatitis/Oral Mucositis

Stomatitis/oral mucositis/mouth ulcers due to everolimus should be treated using appropriate locally available supportive care. Please note that investigators in earlier trials have described the oral toxicities associated with everolimus as mouth ulcers, rather than mucositis or stomatitis. If your examination reveals mouth ulcers rather than a more general inflammation of the mouth, please classify the adverse event as such. Please follow the paradigm below for treatment of stomatitis/oral mucositis/mouth ulcers:

- 1. For mild toxicity (grade 1), use conservative measures such as **non-alcoholic mouth wash or salt water** (0.9%) mouth wash several times a day until resolution.
- 2. For more severe toxicity (grade 2 in which case patients have pain but are able to maintain adequate oral alimentation, or grade 3 in which case patients cannot maintain adequate oral alimentation), the suggested treatments are topical analgesic mouth treatments (i.e., local anesthetics such as benzocaine, butyl aminobenzoate, tetracaine hydrochloride, menthol, or phenol) with or without topical corticosteroids, such as triamcinolone oral paste 0.1% (Kenalog in Orabase[®]).
- 3. Agents containing hydrogen peroxide, iodine, and thyme derivatives may tend to worsen mouth ulcers. It is preferable to avoid these agents.
- 4. Antifungal agents must be avoided unless a fungal infection is diagnosed. In particular, systemic imidazole antifungal agents (ketoconazole, fluconazole, itraconazole, etc.) should be avoided in all patients due to their strong inhibition of everolimus metabolism, therefore leading to higher everolimus exposures. Therefore, topical antifungal agents are preferred if an infection is diagnosed. Similarly, antiviral agents such as acyclovir should be avoided unless a viral infection is diagnosed.

For additional details about the treatment of stomatitis as an everolimus adverse drug reaction (ADR), see the 7904 Study Manual of Procedures.

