7.19 Follow-Up Questionnaires

All medications (other than study drug) and significant non-drug therapies (including physical therapy and blood transfusions) administered after the patient starts everolimus must be listed on the CRF. All AEs and SAEs, regardless of causality will be collected and recorded until the study drug has been discontinued. This information will be collected by phone call at 28 days post-treatment termination and for 8 additional weeks after, as indicated.

At the follow-up time point we will collect information about behavior (CBCL) and motor skills (DCDQ) as well as overall neurocognitive outcome. Parental questionnaires will be sent home and completed by the family of the participant. The questions about overall neurocognitive outcome will be conducted over the phone.

Table 13A: Double-Blind Treatment Phase Study Timeline

Measurement	Performed by	Rationale	Scree n (Visit 1)	Baseline ² (Visit 2)	Month 1 (Visit 3)	Month 2* (Visit 4)	Month 3 (Visit 5)	Month 4* (Visit 6)	Month 5* (Visit 7)	Month 6 (Visit 8)	Follow- up	PRN
Visit Windows				Within 42d of Screen	+/-14d	+/-14d	+/-14d	+/-14d	+/-14d	+/-14d	28d after last visit +/-14d	
Medical History	Clinician	Eligibility	Х	Х	X**	Х	X**	Х	Х	X**	Х	
Clinical Interview	Clinician	Eligibility + Safety	Х	Х	X**	Х	X**	Х	Х	X**		
Inclusion/ Exclusion criteria	Clinician	Eligibility	Х	X								
CGI Scale: Severity & Improvement	ΙĒ	Efficacy		X ³	X**	X ⁵	X**	X ⁵	X ⁵	X**		
Vital Signs	Clinician	Safety	Х	Х	Х		Х			Х		
Physical / Neurological Exam	Clinician	Safety	Х							X**		х
Dermoscopy	Clinician	Efficacy		Х			X**			X**		

Microbiome/ Mycobiome Sample Collection		Efficacy		x			х			х		
Tanner Staging	Clinician	Safety		Х						Х		
Side-effects (CTCAE v5.0 + DOTES)	Clinician	Safety	Х	х	X**	Х	X**	Х	Х	X**	Х	
Laboratory tests ¹	Lab	Safety	Х		Х		Х			Х		Х
Everolimus level (only done after M1 if needed)	Lab	Dose Adjust			х							х
PTEN-associated proteins	Lab	Efficacy	X ⁴	X ⁴			Х			x		
Concomitant treatment log	Clinician	Safety+ Efficacy	Х	Х	Х	Х	Х	Х	X	х	Х	
Autism Diagnostic Interview- Revised	Clinician	Sample Description		х								
Primary Efficacy Outcome Neurocognitive Composite	Clinician	Efficacy		х			x	5		Х	х	
Columbia- Suicide Severity Rating Scale	Clinician	Safety	Х		X**		X**			X**		
Conners' Continuous Performance Test (CPT-3/K- CPT-2)	Clinician	Efficacy	х	х	.0	O	х			х		
Stanford-Binet Fifth Edition (SB- 5) / Mullen Scales of Early Learning (MSEL)	Clinician	Efficacy	Х							x		

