Stanford-Binet Working Memory Subscale Only	Clinician	Efficacy		x			х					
Purdue Pegboard (PP)	Clinician	Efficacy	Х	Х			Х			Х		
Wechsler Processing Speed Index Wide Range	Clinician		2	Х			х			х		
Assessment of Memory and Learning-2 (WRAML-2)	Clinician	Efficacy		х			X**			X**		
Peabody Picture Vocabulary Test – Fourth Edition (PPVT-4)	Clinician	Efficacy		Х			X**			X**		
Expressive Vocabulary Test – Second Edition (EVT-2)	Clinician	Efficacy		x			X**			X**		
Autism Diagnostic Observation Schedule (ADOS-2)	Clinician	Efficacy		х						х		
Social Responsiveness Scale – Second Edition (SRS-2)	Parent Report	Efficacy		х			х			х		

Repetitive Behavior Scale – Revised (RBS-R)	Parent Report	Efficacy	X	Х		Х		
Developmental Coordination Disorder Questionnaire (DCDQ)	Parent Report	Efficacy	x	x		x	x	
Behavior Rating Inventory of Executive Function (BRIEF)	Parent Report	Efficacy	x	Х		X		
Adult/Child Behavior Checklist	Parent Report	Efficacy	x	Х		X	X	
Sensory Profile Questionnaire - Short Form (SPQ)	Parent Report	Efficacy	X	x		х		
Vineland Adaptive Behavior Scales (VABS-III) – caregiver report	Parent Report	Efficacy	x	х		X		
Eye Tracking (Optional)	Clinician	Efficacy	×	х		Х		
Resting State EEG/Auditory Evoked Potentials (Optional)	Clinician	Efficacy	x	x		x		
Participant Unblinding						X**		Х

¹Coagulation testing will only be performed at screening, month 3 and month 6. Pregnancy testing, serum is done at screening and month 6 and urine may be used for onsite visits (if deemed clinically necessary) for women of childbearing potential.

2 Monthly visit windows are calculated based on date of Baseline visit.

CGI: Clinical Global Impressions Scale; IE: Independent Evaluator; CTCAE: Common Terminology Criteria for Adverse Events; DOTES: Dosage Record and Treatment Emergent Symptom Scale; **: primary outcome mesaure only.

Table 13B: Open Label Treatment Phase Study Timeline

	- P	or rioutino			11011110						
Measurement	Performed by	Rationale	Baseline ² (Visit 9)	Month 1 (Visit 10)	Month 2* (Visit 11)	Month 3 (Visit 12)	Month 4* (Visit 13)	Month 5* (Visit 14)	Month 6 (Visit 15)	Follow- up	PRN
Visit Windows			Within 2 weeks of Phase A, Month 6	+/-14d	+/-14d	+/-14d	+/-14d	+/-14d	+/-14d	28d after last visit +/-14d	
Medical History	Clinician	Eligibility	#	X**	X	X**	Х	Х	X**	Х	
Clinical Interview	Clinician	Eligibility + Safety	#	X**	Х	X**	Х	Х	X**		
Inclusion/ Exclusion criteria	Clinician	Eligibility	X								

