CGI Scale: Severity & Improvement	IE	Efficacy	X ³ **	X**	X ⁴	X**	X ⁴	X ⁴	X**		
Vital Signs	Clinician	Safety		Χ		x			Х		
Physical / Neurological Exam	Clinician	Safety							X**		х

³At the baseline visit, only the CGI: Severity scale will be completed.

⁴PTEN-associated protein blood collections will be collected at either the screening or baseline visit (as well as at the 3 month and 6 month visits)

⁵CGI optional for phone interviews month 2, month 4, and month 5.

^{*=} May be performed by phone or in person

^{**=} May be performed by phone/videoconference under extenuating circumstances (note: Physical / Neurological Exam can not be completed in full remotely, but a modified version can be performed)

Dermoscopy	Clinician	Efficacy				X**			X**		
Microbiome/	Jiiiilolaii	Lindacy				^					
Mycobiome Sample Collection		Efficacy				х			x		
Tanner Staging	Clinician	Safety							Х		
Side-effects (CTCAE v5.0 + DOTES)	Clinician	Safety	#	X**	х	X**	х	х	X**	х	
Columbia-Suicide Severity Rating Scale	Clinician	Safety		X**		X**			X**		
Laboratory tests ¹	Lab	Safety	#	Х		Х			Х		Х
Everolimus level (only done after M1 if needed)	Lab	Dose Adjust		х							Х
PTEN-associated proteins	Lab	Efficacy				Х			X	,	
Concomitant treatment log	Clinician	Safety+ Efficacy	#	Х	Х	Х	х	Х	X	Х	
Primary Efficacy Outcome Neurocognitive Composite	Clinician	Efficacy	#			х	O		х	х	
Conners' Continuous Performance Test (CPT-3/K-CPT-2)	Clinician	Efficacy				x			x		
Stanford-Binet Fifth Edition (SB- 5) / Mullen Scales of Early Learning (MSEL)	Clinician	Efficacy							х		
Stanford-Binet Working Memory Subscale Only	Clinician	Efficacy				Х					
Purdue Pegboard (PP)	Clinician	Efficacy				Х			Х		
Wechsler Processing Speed Index	Clinician		30			Х			Х		
Wide Range Assessment of Memory and Learning-2 (WRAML-2)	Clinician	Efficacy				X**			X**		
Peabody Picture Vocabulary Test – Fourth Edition (PPVT-4)	Clinician	Efficacy				X**			X**		
Expressive Vocabulary Test – Second Edition (EVT-2)	Clinician	Efficacy				X**			X**		
Autism Diagnostic Observation Schedule (ADOS-2)	Clinician	Efficacy							х		
Social Responsiveness Scale – Second Edition (SRS-2)	Parent Report	Efficacy				Х			Х		
Repetitive Behavior Scale – Revised (RBS-R)	Parent Report	Efficacy				Х			Х		

Developmental Coordination Disorder Questionnaire (DCDQ)	Parent Report	Efficacy		Х		X	х	
Behavior Rating Inventory of Executive Function (BRIEF)	Parent Report	Efficacy		Х		X		
Adult/Child Behavior Checklist	Parent Report	Efficacy		X		X	X	

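### Section 7.9.1 gives the ADOS-2 to blinded independent evaluators, but Tables 13A and 13B list it under Clinician, and no rule keeps side-effect or assignment information from whoever rates it at Month 6

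*Combined protocol and SAP*

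**What the plan says.** Section 7.9.1 of the protocol: "IEs, who are blind to treatment condition, will rate 3 measures in this study: CGI-S, CGI-I, and ADOS-2". The same section has the independent evaluators (IEs) trained on vignettes for these three measures at the start and yearly, with retraining for anyone who misses the criterion.

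The timelines in Tables 13A (double-blind) and 13B (open-label) have a column for who performs each measure. The CGI row reads "CGI Scale: Severity & Improvement IE Efficacy". The ADOS-2 row reads "Autism Diagnostic Observation Schedule (ADOS-2) Clinician Efficacy" in both tables. The side-effect row reads "Side-effects (CTCAE v5.0 + DOTES) Clinician Safety". The footnotes expand IE as Independent Evaluator, so the tables use IE and Clinician as different labels.

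On blinding, Sections 6.2 and 7.16.8 say that the site team stays blinded throughout. Section 7.6 has the site obtain the unblinded assignment before the Month 6 visit, or before early termination. Table 11 places the ADOS-2 at Baseline and Month 6 only.

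On side effects, Section 6.3 says: "Adverse events most frequently observed with everolimus are stomatitis, mouth ulcers, acne, infection, and menstrual irregularities". Section 6.3.7 tells investigators: "If your examination reveals mouth ulcers rather than a more general inflammation of the mouth, please classify the adverse event as such".

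**The concern.** The ADOS-2 calibrated severity score is a named efficacy endpoint (Section 2.2). Table 12 lists three autism-symptom outcomes, and only the ADOS-2 is scored from observation; the SRS-2 and RBS-R are parent, informant or self report. Its credibility depends on the rater not knowing the arm.

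The safeguard in Section 7.9.1 is the use of trained, blinded evaluators. The schedule, which sites follow day to day, does not carry that safeguard over to the ADOS-2. It uses the label attached to the side-effect review, and everolimus has a recognisable side-effect profile. A rater who knows that a child has had mouth ulcers can form a view about the arm without seeing the code. Section 7.6 adds a more direct route, because the actual assignment reaches the site before the one post-baseline ADOS-2 of the blinded phase.

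Under Section 17.1, a secondary outcome that passes the false discovery rate correction becomes a candidate for Phase III. A rating influenced by knowledge of the arm could therefore feed into a development decision.

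**Working it through.** No figure in the plan depends on this point, so the main check is a comparison of the text.

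**1. Who rates the ADOS-2?**
- Section 7.9.1: blinded IE, trained to reliability.
- Table 13A: Clinician.
- Table 13B: Clinician.
- CGI in the same two tables: IE.

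Section 7.9.1 names three IE measures. CGI-S and CGI-I share one table row and are labelled IE; the third is labelled differently. Nothing in the protocol reconciles this.

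**2. What else does Clinician cover?** In Table 13A it covers medical history, clinical interview, physical and neurological examination, the CTCAE/DOTES review and the concomitant treatment log. It also covers the CPT-3, the Purdue Pegboard, the PPVT-4, eye tracking and EEG. It is a general label. It permits one person to review side effects and score the ADOS-2, but does not require it.

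**3. Is there a separation rule elsewhere?** No section says that the ADOS-2 rater must differ from the person assessing adverse events. Section 7.9.1 calls the IEs blind to treatment but does not withhold adverse-event records, dose changes or everolimus levels from them. The CGI, although labelled IE, has the same gap.

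**4. Which ratings are exposed?**
- Baseline: normally before the first dose (Section 7.7.1 has dosing start within 7 days of that visit), so there are no drug side effects to see.
- Month 6, double-blind: after six months of treatment. The physical examination is scheduled at this visit, and the assignment has been obtained beforehand under Section 7.6.
- Open-label visits: everyone knowingly takes everolimus, so there is no blind to protect. Table 13B shows the label conflict only.

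For the ADOS-2 the exposure is therefore the Month 6 double-blind rating.

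**5. Can the bias be sized?** Only from assumptions. If a rater shifts scores for patients with known mouth ulcers, then

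spurious difference = (everolimus minus placebo proportion with known ulcers) × (rating shift in SD).

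Neither factor is in the documents. Section 6.3.1 classes stomatitis as very common in the pooled tuberous sclerosis studies, which means only at least 1 in 10 and gives no placebo rate. Three assumed cases follow, with rejection rates under no true effect for a one-sided two-sample t test with 18 to 20 per arm. The last column uses .05/15 = .0033, the strictest Benjamini-Hochberg step if there were 15 secondary outcomes; 15 is also an assumption.

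| Assumed excess × shift | Spurious difference | Nominal one-sided .05 | At .05/15 |
|---|---|---|---|
| 0.10 × 0.2 | 0.02 SD | about 5.7% | about 0.4% |
| 0.40 × 0.2 | 0.08 SD | 7.9–8.1% | about 0.7% |
| 0.60 × 0.5 | 0.30 SD | 22.3–23.8% | 3.1–3.5% |

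The spread across rows and columns shows that no single figure can be attributed to this plan.

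**The case against.** The strongest reply is that this is loose table labelling. Clinician is used for almost everything that is not a laboratory test or a parent form. Section 7.9 refers to very experienced testers, and Section 7.22 has a physician evaluate changes and adverse events, so in practice these may be different people. Section 7.9.1 deals specifically with who rates, whereas the table column says who performs. The operations manual that Section 7.9.1 mentions may settle the matter. All of this is fair, and it means that the tables show an opening rather than a breach. The opening still stands, because the protocol gives two answers and the schedule is the one that sites consult.

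A second reply is that correcting the label alone would not blind anyone to mouth ulcers, since an IE could hear of them too. This also stands, and it is why the fix must include a separation rule that covers the CGI.

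A reader might infer three stronger things that the documents do not support:
- *That untrained raters will score the ADOS-2 at Month 6.* Section 7.9.1 requires reliability training on the ADOS-2, and the table label is the same at Baseline and Month 6. Nothing says that an untrained person will rate, or that raters change between the two visits.
- *That sites are directed to inspect every mouth.* Section 6.3.7 tells investigators how to classify what an examination reveals. Section 7.22 schedules full physical examinations only at screening and Month 6, and otherwise as needed.
- *That the false-positive rate rises to some 8–24%.* That range rests on an assumed 40 to 60 point excess of ulcers, an assumed 0.2 to 0.5 SD shift, and a rater who knows of every case. It also uses a nominal .05 test, whereas Sections 17 and 17.1 apply a false discovery rate correction to secondary outcomes.

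**Conclusion.** The contradiction between Section 7.9.1 and Tables 13A and 13B is plain and needs no assumptions. The missing separation rule and the early release of the assignment under Section 7.6 are also in the text.

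The consequence is limited. It is a possible rating bias at Month 6 of the double-blind phase, in one secondary outcome under false discovery rate control, with the same exposure for the IE-rated CGI. It does not touch the primary safety endpoint or the neurocognitive composite, and Section 17 describes the trial as exploratory and mainly descriptive. The risk is real only if the person scoring has, or is given, side-effect, dosing or assignment information; the plan allows this but does not prescribe it. The size of any bias cannot be derived from the documents. This is a cheap improvement worth making, not a flaw that undermines the trial.

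**What to change.** 1. In Tables 13A and 13B, change the performer of the ADOS-2 from Clinician to IE.
2. In Section 7.9.1, add that in the double-blind phase the IE who rates the ADOS-2 and CGI does not carry out the CTCAE/DOTES review, the physical examination or dose-change contact. The IE also does not see those records, the everolimus level or the treatment assignment until the Month 6 ratings are scored and locked.
3. Cross-refer to that sentence in Section 7.6. Staff who prepare open-label dispensing at the Month 6 visit (Section 4.4) can still receive the assignment beforehand, but the IE does not.

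Cost: two table cells, one addition to Section 7.9.1 and a cross-reference. IEs already rate the CGI at Baseline and Month 6, the two ADOS-2 visits, so no new role is needed. The downside is some scheduling effort at the IE-rated visits, mainly for a small site where one person now covers several tasks.

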7.9.2 Research Report

Upon request, participants/parents will be provided with a research report with a summary of assessment scores. This report will be provided at the end of treatment.

7.9.3 Main Efficacy Outcomes

Neurocognitive Composite

A composite neurocognitive score will be generated based on performance on objective measures. The composite index score will be computed in two ways. The first will be an average of measures evaluating working memory (SB-5 working memory subscale), processing speed (CPT-3 mean reaction time), and fine motor skills (Purdue Pegboard Test-average of both hands). The second will include the above average weighted by two-thirds and an average of the remaining standardized, norm-referenced neurocognitive measures (e.g., non-verbal ability, visuomotor skills, verbal learning, receptive and expressive language) weighted by one-third. The first method will be preferred if nearly complete data is observed on the 3 primary constructs (working memory, processing speed, and fine motor skills) in randomized patients. The second will be preferred if missing data is present on >20% of randomized patients. In order for any patient to be included in the study they must complete measures from at least one of the three primary efficacy constructs. If patients cannot complete the full Stanford Binet, the Mullen Scales of Early Learning may be substituted. In a similar

fashion, if the CPT-3 cannot be completed, the processing speed index of the Wechsler scales may be substituted as an alternative measure of processing speed.

Measures were chosen based on previous empirical findings in a cross-sectional cohort study of PTEN patients with ASD. In this study, measures of working memory and processing speed were differentially impaired relative to other cognitive measures, including IQ. Furthermore, the cognitive deficits seen in these patients were related to reduced PTEN protein levels and brain white matter abnormalities. Specifically, in a cross-sectional mediational model, reduced PTEN protein levels led to greater brain white matter abnormalities which, in turn, led to greater cognitive difficulties. Although not evaluated using standardized testing, in our prior cohort of PTEN patients with ASD, every patient had a history of fine motor difficulties, occupational therapy, and/or observations during testing of significant fine motor weaknesses. Motor difficulties are also consistent with brain white matter abnormalities. Thus, the neurocognitive index will include measures that have both empirical and biological bases for inclusion as outcome measures.

In the second version of the neurocognitive composite, the primary justifications for including the remaining neurocognitive measures are: 1) if significant missing data is seen on measure of processing speed, working memory, and fine motor skills, including a minor component of additional neurocognitive measures will ensure more reliably obtained data is contributing to the measurement of change, and 2) PTEN expresses in all of the cells of the body, the brains of PTEN patients showed widespread changes that included white matter abnormalities but also regional gray matter changes, and mouse models of PTEN loss have suggested that dendrite and synaptic dysfunction is also a consequence. Thus, it is reasonable to expect a range of neurocognitive functions might improve. Inclusion of other neurocognitive measures as the minority part of the index will ensure that improvements in other domains, such as expressive language, also have an opportunity to contribute to individual patient outcome measurements. Given that we do not yet know with certainty which neurocognitive functions are most likely to improve in this whole brain condition, allowing for possible improvement in other domains seems prudent.

Use of a neurocognitive composite score has several advantages. Assuming that everolimus treatment does not impair some functions while improving others (an unlikely scenario), a composite score is likely to be highly reliable, can be computed in all patients even if 1 or 2 measurements are missing or could not be completed, and has good domain coverage to capture possible variability across patients in the specific neurocognitive domains showing improvement. An example of the latter advantage, is if some individuals show improvements in processing speed while others show improvements in working memory. The neurocognitive composite would identify improvements in both of these sets of patients. As such, the neurocognitive composite may be more sensitive to change than any individual measure. Furthermore, a composite primary efficacy outcome will not require additional multiple comparison correction.

